## SUMMARY OF CHANGES

Version/Sections	Summary of Changes	Date
Version 9.0	
Pg.10 and Section 3.5: Updated Study Schematic to include Open-label Extension
 
Section 1.2.2: Updated Clinical Experience and removed outdated information from 1.2.2.1 – 1.2.2.7
 
Section 1.3.1 and 3.0: Added the Open-label Extension study design to section 1.3.1 and throughout section 3.0
 
Table 1& 2: Updated the Schedule of Assessments to include an Open-label Extension Phase and footnotes
 
Section 3.5.3 Day-35 and added section 3.5.4 Open-label Extension Phase (Days 36-119) and 3.5.5. Follow-up Safety Visit
 
Section 4.1: Number of subjects who can enter Open-label Extension.
 
Section 5.4: Early Discontinuation who are not eligible to enter Open-label extension phase.
 
Section 6.0: Study Drug/Medication Management to distinguish IP between Double-blind and Open-label, packaging, shipment, storage, administration, and treatment compliance.
 
Section 9.5: Updated schedule of analyses which clarifies the final analysis of the Double-blind phase vs. the study/trial.
 
Corrected inconsistencies and typographical errors throughout protocol
	08-Apr-2022

## STUDY SUMMARY

Title:	BHV3000-202: A Phase 2, Double-Blind, Placebo Controlled, Crossover Trial of BHV-3000 (Rimegepant) for Treatment Refractory Trigeminal Neuralgia
Rationale:	
Trigeminal Neuralgia is a neuropathic pain disorder characterized by recurrent, paroxysmal, lancinating pain in the distribution of one or more branches of the trigeminal nerve. These episodic bouts of severe facial pain can last seconds to minutes, occur several times per day, and often result in significant disability. Although the exact mechanism of action remains unclear, antiepileptic drugs, most notably carbamazepine and oxcarbazepine, remain the first-line treatment for these patients. Nonetheless, the majority of patients have an incomplete response to current pharmacotherapy and resort to more invasive procedures, including rhizotomy and surgical decompression of the microvasculature surrounding the trigeminal nerve. While numerous treatment options exist, inadequate relief of pain and recurrence of symptoms are common, prompting the need for novel pharmacologic interventions.
 
Although the underlying mechanisms of classical Trigeminal Neuralgia have not been fully elucidated, imaging studies and surgical procedures clearly implicate vascular compression of the trigeminal nerve in the pathophysiology of the disease. As a result of this nerve compression, subsequent axonal demyelination of the trigeminal nerve results in hyperexcitation and abnormal discharge of primary sensory neurons, ultimately contributing to the aberrant nociceptive transmission and neuropathic pain associated with this disorder. The neuropeptide Calcitonin Gene-Related Peptide (CGRP) and its aberrant release from the trigeminal nerve has been clearly implicated in the pathophysiology of migraine headache. In addition, CGRP is thought to play an important role in the development of neuronal sensitization and neuropathic pain and is a major mediator of pathologic vasodilatation of intracranial arteries. Clinical studies have also shown increased levels of CGRP in the cerebrospinal fluid of patients with Trigeminal Neuralgia.
 
The proposed study is based on the evolving preclinical and clinical evidence suggesting a role for CGRP in the development of neuropathic pain syndromes and Trigeminal Neuralgia. BHV-3000 (rimegepant) is a small molecule CGRP receptor antagonist that is being developed for the potential treatment of Trigeminal Neuralgia. The data from this study will assess the safety and efficacy of rimegepant vs placebo in the treatment of Trigeminal Neuralgia.

Target Population:	The study will recruit male and female patients 18 years of age and older with a clinical diagnosis of classical or idiopathic Trigeminal

[figure not shown]
[figure not shown]
	
Neuralgia based on the International Classification of Headache Disorders, 3rd edition, who have had an inadequate response, intolerance, or contraindication to current treatments and symptoms for at least three months. Additionally, patients must have neuroimaging to exclude a secondary cause of the neuralgia and a mean of <math>\geq 4</math> on the daily “average intensity”, on an 11-point Numerical Pain Rating Scale (0-10) during the 14- 30 day screening period.

Number of Subjects:	
Approximately 120 patients will be screened to randomize 60 patients in a 1:1 ratio into 2 treatment sequences receiving 75 mg rimegepant vs Placebo, using a 2-period, 2-sequence, crossover design.

Objectives:	
The primary objective of the study is to evaluate the efficacy of rimegepant compared to placebo in providing symptomatic pain relief in patients with Trigeminal Neuralgia as measured by a reduction from baseline in the average daily Numeric Pain Rating Scale.
 
The secondary objectives of the study will be:
 

• To assess the safety and tolerability of rimegepant relative to placebo in patients with Trigeminal Neuralgia

• To evaluate the efficacy of rimegepant vs placebo for improving physical function in Trigeminal Neuralgia patients as measured by the Penn Facial Pain Scale-Revised

• To evaluate the efficacy of rimegepant vs placebo for improving functional disability in Trigeminal Neuralgia patients as measured by the Pain Disability Index

• To evaluate the efficacy of rimegepant vs placebo on global functioning as measured by the Patient Global Impression of Change Scale.

• To evaluate the efficacy of rimegepant vs placebo in providing symptomatic pain relief as captured by daily rating of worst pain episode as measured by the 11-point Numeric Pain Rating Scale

• To evaluate the efficacy of rimegepant vs placebo in providing symptomatic pain relief of clinical importance as defined by a 2-point or greater reduction in the 11 point Numeric Pain Rating Scale

	CCI
Study Design:	
BHV3000-202 is a phase 2, multi- center, double-blind, placebo controlled, crossover trial to assess the safety, tolerability, and efficacy of rimegepant in treating Trigeminal Neuralgia in patients who failed to respond adequately to or had intolerance or a contraindication to pharmacotherapy. Current inadequate response to therapy is defined by a daily pain score of greater than or equal to 4 on the “average intensity”, on the 11 point Numerical Pain Rating Scale during the 14 days prior to baseline. A crossover design with a placebo washout period of 7 days between treatments will be used due to the limited number of subjects, with each patient serving as their own control. The study will be conducted at multiple centers.
 
Prior to randomization, patients will enter a 14-30 day screening period during which they will complete daily self-reported assessments of pain intensity over a 24 hour period using an 11 point Numeric Pain Rating Scale, ranging from 0 (for no pain) to 10 (for the worst imaginable pain.) Throughout the study, patients will be allowed to remain on their current medication regimens, provided they are on a stable dose for a minimum of 4 weeks prior to randomization visit.
 
Patients with a mean of <math>\geq 4</math> on the daily “average intensity” on the 11 point Numeric Pain Rating Scale, during the 14-30 day screening period, will be randomized to one of two treatment sequences to receive rimegepant 75 mg immediate release (IR) tablet administered orally vs placebo. Each sequence will include a 2 week treatment phase, with daily dosing of study drug/medication or placebo. This will be followed by a 7 day placebo washout period. After the placebo washout period, another 2 week treatment phase will follow, again with once daily dosing of study drug/medication or placebo. In the first sequence, patients will receive placebo for the first treatment period and rimegepant 75 mg IR tablet during the second treatment period. The second sequence will have rimegepant 75 mg IR tablet during the first 2 week treatment period, followed by placebo in the second treatment phase. For subjects, this design should seem like a “seamless” 5 week treatment phase.
 
During each 2 week treatment phase and during the 7 day placebo washout period, patients will complete the 11 point Numeric Pain Rating Scale daily, as described above. In addition, patients will complete a paper diary daily to record efficacy data. The diary will include the daily recording of overall pain using the 11 point numeric pain rating scale, a recording of daily use of rescue medications, and a daily rating of worst pain episode using the 11 point Numeric Pain Rating Scale. This data will be entered into the CRF. Other secondary


	
endpoints will be assessed at the beginning and end of each treatment period, including the Penn Facial Pain Scale (a 12-item activities of daily living scale designed to specifically assess the impact of Trigeminal Neuralgia symptoms on daily activities), the Pain Disability Index (which measures the degree to which chronic pain interferes with 7 categories of daily activities, measured on a 11 point scale ranging from 0 (no disability) to 10 (worst disability). The Patient Global Impression of Change (PGIC: a patient self-reported global index scale) will be assessed at the end of each treatment sequence. In addition, the Sheehan-Suicidality Tracking Scale (S-STS) will be administered as a safety measure at screening, as well as at every visit, as specified in the protocol.
 
In addition, subjects completing the Double-Blind Phase of the study and who continue to meet inclusion/exclusion criteria may be offered up to 12 weeks of Open-Label Extension treatment, provided the Principal Investigator (PI) believes open-label treatment offers an acceptable risk-benefit profile. Subjects who agree to enter the Open-Label Extension Phase will not be required to have a wash-out period of drug, but instead should continue dosing as specified in the Open-Label Extension Phase.
 
All subjects will undergo a post study Follow-up Safety Visit 14 days after the final EOT Visit and last dose of study drug/medication administration. Subjects who discontinue from the study at any time during either the Double-Blind Phase or the Open-label Extension Phase are expected to complete the End of Treatment (day 119) Visit and the 2-Week Follow-up Safety Visit.

Primary Endpoint:	Improvement of Trigeminal Neuralgia symptoms as assessed by the Numeric Pain Rating Scale over the 2-week treatment period
Secondary Endpoints:	

• The frequency of unique subjects with adverse events, serious adverse events, adverse events leading to discontinuation, Sheehan Suicidality Tracking Scale (S-STS) total score and clinically significant laboratory and ECG test abnormalities, from case report forms and clinical laboratory evaluations

• Penn Facial Pain Scale-Revised (Penn-FPS-R)

• Pain Disability Index

• Patient Global Impression of Change Scale (PGI-C)

• Measurement of worst pain in a 24-hour period using the Numeric Pain Rating Scale

• Achievement of at least a 2-point reduction in average daily Numeric Pain Rating Scale score

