(d) Height measured at Screening Visit only. Weight, body temperature, respiration rate, blood pressure, and heart rate will be collected at all timepoints where indicated. Sitting arterial systolic and diastolic blood pressure and radial artery pulse rate will be measured.

(e) SAEs, AEs and concomitant Procedures must be reported after subject signs informed consent. SAEs should be reported from signing of consent through the 14 day follow up safety visit. Non-serious AEs should be reported from the baseline visit to the safety follow up visit.

(f) Subjects must take their study drug/medication every day, regardless of whether or not they have Trigeminal Neuralgia pain. Subjects must report each tablet they take on the paper diary. Due to the COVID-19 Pandemic, study drug/medication may be shipped to a subject, with up to an 2-week supply. Proper documentation must be maintained in the subject's source records including shipping vendor, tracking number, confirmation of receipt by subject, and all other relevant information.

(g) Subjects with 2 or more missed daily paper pain diaries during the Screening Period should be considered for discontinuation from the study for poor compliance, after discussion with sponsor. Subjects in the Double-Blind Treatment Period who demonstrate poor compliance will be discussed with the Sponsor and corrective training will be complete by the site with the subject.

(h) The paper diary will be dispensed at the Screening Visit, after all Screening Procedures are completed. The subject will be trained on the use of the paper diary. The subject will use the paper diary every day during the Screening and Double-Blind Phases to report Trigeminal Neuralgia pain, medication use and study drug/medication dosing (Double-BlindTreatment Phase only).

(i) Subjects who do not complete the Double-Blind Treatment Phase should completed the End of Treatment Visit and the 14 day Follow-up Safety Visits (they should not enter the Open-label Extension Phase).

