## **5.4      Early Discontinuation from the Study**

Subjects MUST discontinue investigational product (and non-investigational product at the discretion of the investigator) for any of the following reasons:

- Withdrawal of informed consent (subject's decision to withdraw for any reason)
- Any clinical adverse event (AE), laboratory abnormality or intercurrent illness which, in the opinion of the investigator or sponsor, indicates that continued participation in the study is not in the best interest of the subject
- Pregnancy
- Termination of the study by Biohaven Pharmaceuticals
- Loss of ability to freely provide consent through imprisonment or involuntary incarceration for treatment of either a psychiatric or physical (e.g., infectious disease) illness
- Please see section [5.2.8](#) for guidance on study discontinuation based on results from the S-STS.
- Subjects who discontinue early from the Double-Blind Phase are not eligible to enter the Open-label Extension Phase.

All subjects who discontinue should comply with protocol specified Follow-Up Safety Visit procedures as outlined in [Table 1](#) or [Table 2](#). The only exception to this requirement is when a subject withdraws consent for all study procedures, lost to follow up or loses the ability to consent freely (i.e., is imprisoned or involuntarily incarcerated for the treatment of either a psychiatric or physical illness).

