3.2 Estimands

An estimand is the target of estimation to address the scientific question of interest posed by a study objective. The 4 attributes of an estimand include the population of interest, endpoint of interest, specification of how intercurrent events are reflected in the scientific question of interest, and the summary for the endpoint.

For all objectives, the population of interest is defined through appropriate inclusion/exclusion criteria to reflect the targeted patient population for approval. Refer to the protocol for inclusion/exclusion criteria.

Intercurrent Events

Intercurrent events are those that occur after treatment initiation and either preclude observation of the endpoint or affect its interpretation. The following will be considered intercurrent events:

- Study drug discontinuation before the time point of interest defining the endpoint.
 - For safety objectives:
 - For AEs, study drug discontinuation is handled with a “while-on-treatment strategy,” i.e., response to treatment prior to the occurrence of the intercurrent event of interest, such that all observed values of the endpoint of interest will be used prior to study drug discontinuation.
 - For all other safety endpoints, study drug discontinuation is handled with a “treatment policy strategy”, i.e., the occurrence of the intercurrent event will be considered irrelevant, such that all observed values of the endpoint of interest will be used regardless of study drug discontinuation.
 - For efficacy objectives:
 - For the NPRS objectives, study drug discontinuation is handled with a “while-on-treatment strategy”.
 - For the Penn-FPS-R, PDI, and PGI-C efficacy objectives, study drug discontinuation is handled with a “treatment policy strategy”.
 - For all other objectives (i.e., use of non-study TN standard of care medications on or before the time point of interest), this intercurrent event will be handled with a “while-on-treatment strategy”

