3.2.2 Secondary Objective Estimands

Table 2 presents the estimands for secondary objectives.

Table 2: Secondary Objective Estimands

Objective 1	To assess the safety and tolerability of rimegepant relative to placebo in patients with TN
Safety Endpoint	Frequency of unique subjects with: SAEs, AEs leading to discontinuation, AEs judged to be related to study medication, S-STS total score, and clinically significant electrocardiogram (ECG) and laboratory abnormalities observed during the randomization phase of the study
Summary	Using the treated subjects population: 
Number and percentage of subjects with these events or findings
Intercurrent Events	Study drug discontinuation: while-on-treatment strategy for AEs; treatment policy strategy for all other safety endpoints
Objective 2	To evaluate the efficacy of rimegepant vs placebo for improving physical function in TN patients as measured by Penn-FPS-R
Efficacy Endpoint	Change in Penn-FPS-R total score from baseline to the end of the 2-week treatment phase of the study
Summary	Using the mITT population: 
Descriptive statistics for Penn-FPS-R and change from baseline as a continuous variable by treatment group at each visitDifference in mean change from baseline in Penn-FPS-R scores between treatment groups estimated using MMRM
Intercurrent Events	Study drug discontinuation: treatment policy strategy
Objective 3	To evaluate the efficacy of rimegepant vs placebo for improving functional disability in TN patients as measured by the Pain Disability Index
Efficacy Endpoint	Change in Pain Disability Index total score from baseline to the end of the 2-week treatment phase of the study
Summary	Using the mITT population: 
Descriptive statistics for Pain Disability Index and change from baseline as a continuous variable by treatment group at each visitDifference in mean change from baseline in Pain Disability Index between treatment groups estimated using MMRM
Intercurrent Events	Study drug discontinuation: treatment policy strategy
Objective 4	To evaluate the efficacy of rimegepant vs placebo on global functioning as measured by the PGI-C
Outcomes Research Endpoint	PGI-C Scale at the end of the 2-week treatment phase of the study

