6 STATISTICAL ANALYSES

6.1 General

6.1.1 *Programmed Output*

A list of TLFs and corresponding templates are presented separately in a mock TLF document corresponding to this SAP.

Refer to the Core SAP for additional details about programmed output.

Medical history and AEs are coded using the Medical Dictionary for Regulatory Activities (MedDRA) most recent version available.

Concomitant medications are coded using the World Health Organization Drug Global Dictionary (WHODrug Global), most recent version available.

All statistical analyses will be performed using SAS statistical software (Version 9.4 or higher), unless otherwise noted.

6.1.1.1 *Tables*

Tables will be summarized by treatment sequence and period, rimegepant pooled, placebo pooled, and overall. Exceptions are specified in subsequent sections as needed.

6.1.1.2 *By-Subject Listings*

By-subject listings will present all data by randomization status (randomized, not randomized), site-subject ID, and additional variables such as time points, as applicable. Listings display as-randomized treatment sequence abbreviated as (1) “RMG-PBO” for Sequence 1 subjects, “PBO-RMG” for Sequence 2 subjects, and (2) “NRND” for subjects who are not randomized.

Refer to the Core SAP for additional details about listings.

6.1.2 *Statistical Methods*

Refer to the Core SAP for descriptive statistics in summary tables, counting rules in frequency tables, and rounding rules.

Categorical variables will be tabulated with the count and percentage within each category (with a ‘Missing’ category if applicable). Continuous variables will be summarized with univariate statistics (e.g., n, mean, median, standard deviation (SD), minimum, and maximum).

Tabulations of the following endpoints present the number of unique subjects with an event: protocol deviations; non-study medications; AEs; and laboratory abnormalities. Thus, for these endpoints, multiple occurrences of the same event are counted only once per subject.

6.1.3 *Handling of Missing Data*

Unless otherwise noted, efficacy analyses will be based on observed data only. For the main analyses of efficacy for primary and secondary endpoints, no imputation will be performed to impute data following discontinuation from study.

For efficacy analyses, partial or missing dates will not be imputed. The relative study days, where determined, will be calculated for full dates only.

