7.2 Analysis Periods

Analysis periods are defined as follows:

- Efficacy endpoints
 - On-DBT efficacy: This period is used to assess efficacy during the DBT Phase, and is abbreviated as “DBT” in the efficacy listing.
 - On-OL rimegepant efficacy: This period is abbreviated as “OLRMG” and used only in the efficacy listing.
 - Follow-up efficacy: This period is abbreviated as “FU” and used in the efficacy listing.
- Pretreatment characteristics and safety endpoints
 - Pretreatment: This period is abbreviated as “PRETRT” in listings, and is used to derive baseline values and to assess pretreatment safety endpoints.
 - Pre-OL rimegepant: This period is used to derive the OL rimegepant baseline value.
 - Pre-DB or OL rimegepant: This period is used to derive the DB or OL rimegepant baseline value.
 - On-DBT safety: This period is abbreviated as “DBT” in safety listings, and is used to assess safety endpoints on DBT for the DBT treated analysis set
 - Post-DBT pre-OL rimegepant safety: This period is abbreviated as “INT” in safety listings, and is used to assess safety endpoints during the interim period (i.e., post-DBT pre-OL rimegepant) for the interim treated analysis set.
 - On-OL rimegepant safety: This period is abbreviated as “OLRMG” in safety listings, and is used to assess safety endpoints for the OL rimegepant treated analysis set.
 - On-DB or OL rimegepant safety: This period is used to assess safety endpoints on DB or OL rimegepant treatment for the DB or OL rimegepant treated analysis set
 - Follow-up safety: This period is abbreviated as “FU” in safety listings, and is used to assess safety endpoints during follow-up.
- Outcomes research endpoints
 - DBT outcomes research: This period is abbreviated as “DBT” in outcomes research listings, and used to assess outcomes research endpoints during the DBT Phase
 - OL rimegepant outcomes research: This period is abbreviated as “OLRMG” in outcomes research listings, and used to assess outcomes research endpoints during the OLE Phase.

For endpoints using the “treatment strategy policy”, analysis period 1 is defined as the Day 14 CRF visit, analysis period 2 is defined as the Day 35 or Day 35/ET CRF visit.

For endpoints using the “while-on-treatment strategy”:

- For AEs, refer to Section 6.4.1 for analysis period definitions.

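### SAP claims a treatment-policy effect for Penn-FPS-R, PDI and PGI-C, but the protocol plans no period-end follow-up after study drug is stopped

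*Protocol*

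**What the plan says.** SAP 3.2 sets the strategy: "For the Penn-FPS-R, PDI, and PGI-C efficacy objectives, study drug discontinuation is handled with a" treatment-policy strategy. It explains that under this strategy "all observed values of the endpoint of interest will be used regardless of study drug discontinuation". SAP Table 2 repeats the choice for Objectives 2 to 4 and fixes the time point. For the first scale the endpoint is "Change in Penn-FPS-R total score from baseline to the end of the 2-week treatment phase of the study"; the Pain Disability Index (PDI) and PGI-C endpoints have the same time point.

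The protocol describes what happens to a subject who stops. Section 5.4, which is headed as early discontinuation from the study, opens its list with "Subjects MUST discontinue investigational product (and non-investigational product at the discretion of the investigator) for any of the following reasons" and sends all who discontinue to the follow-up safety procedures. Footnote (i) of Protocol Table 1 says: "Subjects who do not complete the Double-Blind Treatment Phase should completed the End of Treatment Visit and the 14 day Follow-up Safety Visits". The rule in the Study Summary begins "Subjects who discontinue from the study at any time during either the Double-Blind Phase or the Open-label Extension Phase are expected to complete"; the visits that it then names are End of Treatment (EOT) and the two-week safety visit. Protocol Table 2 marks all three scales at EOT and none of them at the safety visit.

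On the analysis side, SAP 7.2 states for these endpoints that "analysis period 1 is defined as the Day 14 CRF visit, analysis period 2 is defined as the Day 35 or Day 35/ET CRF visit". SAP 6.1.3 states that "no imputation will be performed to impute data following discontinuation from study". The mITT set (Protocol 9.3, SAP 4.1) requires a baseline and a post-baseline efficacy assessment in each sequence. Since a subject is randomized to only one sequence, this presumably means each period.

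**The concern.** A treatment-policy effect at period end needs the score at that time from subjects who stopped drug as well as from those who continued. If the scores of those who stopped are neither collected nor modelled, the contrast answers a different question from the one stated.

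This affects interpretation. The SAP will not evaluate significance, so the differences in LS means and their confidence intervals are the result, and SAP Section 8 puts every analysis in the SAP into the study report. A reader who sees treatment policy will take these differences to cover patients who could not continue. If benefit fades after stopping, the reported difference would be larger than the effect that the label names.

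**Working it through.** **The plan's own figure.** The only quantitative planning is for the NPRS (Protocol 9.2, SAP 5): 60 randomized, 20% dropout, difference 2, SD of the paired difference 3.8, two-sided alpha 0.05.
- Pairs: 60 × (1 − 0.20) = 48.
- Normal approximation: 2 / (3.8/√48) − 1.96 = 3.646 − 1.960 = 1.686, so power is 95.4%. The noncentral t gives 94.6%.

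The stated power above 90% reproduces. The documents give no SD or effect for the three scales, so only the 20% dropout carries over, as an illustration.

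**Where a stopper's scores go.** The visit windows are Day 14 ± 2 and Day 35 −2/+5 (Protocol Table 1). For a subject who stops drug and leaves:
- *In period 1, before the Day 14 window.* The scales are taken once, at EOT, near the stop. There is no Day 14 CRF visit, so period 1 has no score under SAP 7.2. Read literally, the ET score falls under period 2, a treatment that the subject never received. With no second-period assessment, the mITT rule tends to remove this subject.
- *Within the Day 14 window.* The score can be in window and count for period 1.
- *In the washout, after Day 14.* Period 1 has a score. Read literally, the ET score would supply period 2, although the second treatment was not started.
- *In period 2, before Day 33 (35 − 2).* The ET score is used for period 2 but is taken around the stop. Penn-FPS-R asks about the past week (Protocol 5.3.2), so it can largely describe time on drug.
- *Within the Day 35 window.* The score can be in window.

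Only stops close to a scheduled visit yield a score at the time the endpoint names. The later safety visit does not fill the gap. Protocol 3.5.5 mentions unspecified pain scales there, Protocol Table 2 marks none of the three, and SAP 7.2 does not use that visit for these endpoints.

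**Possible size.** Let d be the share of rimegepant periods stopped early, and f (between 0 and 1) the fraction of the on-drug effect still present at period end in those who stopped. With no offset from stopping on placebo:
- Treatment-policy effect = on-drug effect × [1 − d(1 − f)].
- Overstatement by an on-drug estimate = 1 / [1 − d(1 − f)] − 1.

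| d | f = 1 | f = 0.5 | f = 0 |
|---|---|---|---|
| 0.10 | 0% | 1/0.95 − 1 = 5.3% | 1/0.90 − 1 = 11.1% |
| 0.20 | 0% | 1/0.90 − 1 = 11.1% | 1/0.80 − 1 = 25% |

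Both d and f are assumptions. The planned 20% dropout is 0.20 × 60 = 12 subjects over both treatments and both periods, so placing all of it in rimegepant periods is an extreme allocation. The formula also treats the reported estimate as purely on-drug, whereas some ET scores enter it.

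**The case against.** The strongest reply is that the SAP does what it says. Its definition of treatment policy is to use every observed value whether or not drug was stopped, and the CRF-visit rule does so. Values lost because a subject left the study are missing data, which SAP 6.1.3 covers separately. The strategies for Penn-FPS-R and PDI were also revised deliberately in SAP version 2.0. This stands as far as it goes: no collected score is discarded merely because drug was stopped. But the endpoint is set at period end, the design does not plan to obtain that score from those who stop, and no imputation or sensitivity analysis stands in for it. Using all observed values does not then give the effect that the label names.

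Three stronger readings are tempting, and the documents do not support them.
- *That no off-drug period-end score can exist.* All three scales are taken at EOT, the SAP uses ET scores, and a stop near Day 14 or Day 35 can fall in window. The link from stopping drug to leaving the study is also implied by Section 5.4 and footnote (i), not stated as a rule. The Study Summary sentence concerns leaving the study. Protocol 4.4 (item 10) mentions stopping dosing without mentioning exit, and Protocol 8.2.3 leaves trial discontinuation to case-by-case instruction.
- *That non-adherence is wholly excluded.* Under Protocol 6.4, subjects below 80% compliance in the double-blind phase are re-counselled and kept out of the extension, but are not removed from the double-blind phase. Their period-end scores count.
- *That the effect is overstated by 25%.* That figure stacks several worst-case assumptions.

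The consequence is also limited: these are secondary endpoints, they will not be tested, and the study ended early for low enrollment (SAP Sections 1 and 5).

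**Conclusion.** The label and the planned data do not match. For Penn-FPS-R, PDI and PGI-C the estimates will reflect subjects still under observation at period end, plus ET scores taken around stopping, in a population that tends to lose those who stopped in period 1. That is not the treatment-policy effect at period end. Separately, SAP 7.2 needs a rule for ET scores, because its literal wording can credit a score to a treatment never taken.

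The direction and size of any bias are unknown. With f between 0 and 1, overstatement is 0% if benefit persists off drug. It reaches about 11% or 25% only if 10% or 20% of rimegepant periods are stopped, all benefit is gone by period end, and placebo stopping offsets nothing. None of these conditions is a document figure. Type I error and power are not at issue. The point concerns what the reported differences may be said to mean, and it is worth correcting because the correction is cheap.

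**What to change.** **(a) Change the description to fit the data.** In SAP 3.2, SAP Table 2 and SAP 7.2:
- describe these three estimands as based on observed period-end or ET scores, not as treatment policy;
- assign each ET score to the period and treatment in which the subject stopped, and state how an ET score from the washout is handled, so that none is credited to a treatment not started;
- keep the CRF-visit rule for completers. An exposure-date cut like that for the NPRS could discard valid Day 35 scores, because that visit follows the final dose (Protocol 3.5.3) and its window runs to +5 days;
- report, by treatment and period, how many subjects lack a scheduled period-end score.

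The cost is SAP wording, one derivation rule and one table, and the claim becomes narrower.

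**(b) Keep treatment policy and collect the data, if collection is still possible.** Subjects who stop drug without withdrawing consent would complete the three scales at the scheduled end of that period, and mITT would retain subjects with data from one period only. The cost is one extra set of questionnaires for a few subjects. Protocol 3.5.2 would need extending, because it allows remote contact at Day 14 but requires Day 35 and EOT in person. After the 1Q2023 termination this route is probably moot, which leaves (a) as the practical choice.
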